#### **9.5.4 Handling and Shipping of Frozen Tumor for tumor concentration and EGFR phosphorylation**

Neurosurgeons at all participating sites are trained in the collection of biospecimens for pharmacokinetic and pharmacodynamic analyses. Tumor samples will be frozen within 5 min of collection.

The research nurse will notify the laboratory of scheduled sample collections, preferably giving at least 24-h notice, to allow sufficient time to set up laboratory supplies, collect relevant clinical information, and ensure rapid transport of specimens to the laboratory for placement at -80°C (or lower) after collection.

Promptly after excision, rinse the tissue with ice-cold phosphate buffered saline and gently blot on Whatman filter paper to remove surface fluid. Place the tissue into pre-chilled 2.0 mL cryogenic tubes (Fisher catalogue no. 12-565-291). The label must contain the patient ID no. and information identifying the region from which the tissue was excised. Snap freeze the specimen by placing the tube in liquid nitrogen or a dry ice/ethanol bath and record the time of freezing in the Batch Record. Calculate the total time elapsed from biopsy collection to biopsy freezing and record the total number of minutes and seconds elapsed in the Batch Record. Samples will be transferred to a -80°C freezer or liquid nitrogen tank for storage until shipment to the PD processing laboratory. Record the date and time specimens are placed at -80°C.

Just prior to shipment, specimen tubes will be placed into an 81-place freezer box and then in a shipping container with sufficient dry ice to maintain the samples at -20°C for at least 72 hours. Specimens will be shipped via FedEx for delivery by 10 AM the next day (FedEx First Overnight). Seal the box and print and attach the shipping address onto the outside of the shipping container and label the contained as containing biohazardous specimens. Record the shipping date, time, tracking number, and shipping information in the Batch Record. Notification of the delivery must be made by e-mail to both [name] (email: [[contact]](mailto:[contact])) and [name] (e-mail: [[contact]](mailto:[contact])). Include the name of the courier and the tracking no. in the email.

**Ship all frozen tumor samples to:**

[name]  
Memorial Sloan Kettering Cancer Center  
[name]  
[name]  
[name]  
Telephone: + 1 [contact]  
Fax: + 1 [contact]

Once specimens arrive at the [name] laboratory, they will be immediately placed at -80°C (or lower). [name] group will collect all samples, cut a 5 µM section from each specimen and then perform H&E staining. Histopathological review of the H&E stain will be performed by a board-certified neuropathologist at Memorial Sloan-Kettering Cancer Center. Only samples with a tumor cell content > 80 % as determined by a pathologist will be used for further analyses. Each frozen tumor specimen that

passes histopathological Q/C will be split into two samples, one for the determination of intratumoral lapatinib concentrations (Section [9.5.5](#)) and one for the determination of EGFR phosphorylation (Section [9.5.6](#)).

### **9.5.5 Tumor Samples for Intratumoral Drug Distribution: Group A**

The specimens for the determination of intratumoral lapatinib concentration will be shipped to the ABTC Pharmacokinetics Center by the [name] Laboratory following the shipping guidelines in Section [9.5.3](#). The concentration of lapatinib in study samples will be determined by the ABTC Pharmacokinetics Center using an LC-MS/MS assay, also described in Section [9.5.3](#).

Biopsy specimens selected for drug concentration measurement should be at least 0.05 cm^3 (50 mg) intact sections of tumor tissue. To the extent possible, at least one biopsy sample should be resected from a contrast enhancing region of the tumor and another from a non-contrast enhancing region for drug level analysis. These samples must be clearly identified accordingly.

Intratumoral lapatinib concentrations will be measured in fresh frozen tumor aliquots in two batches.

- the first batch of samples (patients # 1-8) will be used for the interim futility analysis and will be run after the initial eight patients. Study enrollment will continue if three or more of these eight tumor samples show an intratumoral lapatinib concentration of > 1.5 μM.
- the second batch of tumor samples (patient # 9-18) will be performed after enrollment has been completed.

Lapatinib concentrations in plasma at the time of tumor resection will also be determined (Section [9.5.3](#)) and this data will be used to calculate a lapatinib tumor/plasma ratio.

### **9.5.6 Tumor Samples for Determination of EGFR phosphorylation in Tumor Tissue: (Group A and Reference Group)**

Determination of EGFR protein levels and EGFR phosphorylation will be performed in the [name] Laboratory. Samples will be lysed in sample buffer with protease and phosphatase inhibitors which has been optimized by MesoScale Discovery to minimize decay of the protein and phosphosignal (<http://www.mesoscale.com>). All clinical trial samples will be run through the mesoscale electrochemiluminescent assay in a single batch. Residual samples will be aliquoted and frozen. All specimens will be handled and stored to minimize decay of the phospho-signal. Further Details regarding the EGFR Mesoscale Assay are provided in [Appendix IV](#). Performance characteristics of this pharmacodynamic assay will be validated in additional laboratory experiments and presented for CTEP review before the specimens from the trial are analyzed.

### 9.5.7 Tumor Sphere Cultures

Glioma Tumor Sphere Lines will be prepared from fresh tumor samples whenever possible (i.e., if there is 500 mg or more of additional enhancing tissue) at each participating ABTC site. The consortium has successfully derived glioma tumor sphere cultures in the context of a prior clinical trial (ABTC 0906).

Whenever possible, at least 500 mg grams of viable tissue will be processed for neurosphere studies. The sterility of the specimen should be preserved while it is minced gently into 0.5 cm cubes in the operating room which optimizes conditions for cellular survival, prevents tube breakage/leakage, and maintains cells at low temperature while avoiding freezing of cells. In brief, a pre-labeled 25cc tube should be filled to the top with a low-glucose, serum-free, buffered transport medium and **placed immediately on wet ice in the operating room**. The specimen should then be inserted into a protective tube to prevent breakage, sealed in a Ziploc bag, and packed **on wet ice** in a pre-labeled styrofoam container with relevant identifying information. The starting and ending times of resection should be noted by personnel at the institution and included in the specimen identification form.

**Specimens for tumor sphere cultures must be shipped immediately from the participating ABTC site to the [name] Laboratory.** Specimens will be shipped via FedEx on the same day for delivery by 10 AM the next day (FedEx First Overnight). Seal the box and print and attach the shipping address onto the outside of the shipping container and label the container as containing biohazardous specimens. Record the shipping date, time, tracking number, and shipping information in the Batch Record.

Notification of the delivery must be made by e-mail to both [name] (email: [[contact]](mailto:[contact])) and [name] (e-mail: [[contact]](mailto:[contact])). Include the name of the courier and the tracking no. in the email.

**Ship all tumor samples to:**

[name]  
Memorial Sloan Kettering Cancer Center  
[name]  
[name]  
[name]  
Telephone: + 1 [contact]  
Fax: + 1 [contact]

Upon receipt, the specimen will be immediately logged into the Oncore database and transported to the [name] laboratory. Within 20 minutes of **arrival at the [name] Laboratory**, sterile, refrigerated specimens will be processed into neurosphere cultures. Tumor specimen samples are washed in cold PBS twice, then manually dissociated and placed in Accumax (Innovative Cell Technologies) for 15 min under sterile conditions. Cells are subsequently washed and filtered through a 100- $\mu$ m

strainer and plated in NeuroCult NS-A proliferation media (Stemcell Technologies) supplemented with 10 ng/mL rhbFGF for all experimental conditions in the study. Initial cultures are also supplemented with 20 ng/mL rhEGF. Cells are incubated at normal oxygen levels at a temperature 37.0 °C and 5% CO2 (Szerlip et al. 2012).

Lapatinib sensitivity will be determined in the [name] Lab using a Trypan Blue Exclusion Assay (Vivanco et al. 2012).

## 10.0 OFF TREATMENT/OFF STUDY CRITERIA

Each subject has the right to withdraw from the study at any time without prejudice. The investigator may discontinue any subject's participation for any reason, including adverse event or failure to comply with the protocol (as judged by the investigator such as compliance below 80%, failure to maintain appointments, etc.).

Should a subject withdraw from the study, the reason(s) must be stated on the case report form, and a final evaluation of the subject should be performed.

Patients who go off treatment must be followed for adverse events (AEs) for at least 30 days from the last dose of lapatinib.

### 10.1 Off Treatment Criteria

1. Disease Progression: Remove patient from protocol therapy at the time progressive disease is documented. Disease progression is defined as: Progressive neurologic abnormalities not explained by causes unrelated to tumor progression (e.g. anticonvulsant or corticosteroid toxicity, electrolyte abnormalities, hyperglycemia, etc.) or a greater than 25% increase in the measurement of the tumor by MRI scan. If neurologic status deteriorates, on a stable or increasing dose of steroids, or if new lesions appear on serial MRI, further study treatment will be discontinued
2. Adverse Event:
  - Intercurrent illness that prevents further administration of treatment
  - Patients who experience unacceptable toxicity. Patients removed from study for unacceptable adverse events will be followed until resolution or stabilization of the adverse event.
3. Patient Withdrawal: Patient's refusal to continue treatment: in this event, document the reason(s) for withdrawal.
4. Non Compliance: Failure to comply with protocol (as judged by the investigator such as compliance below 80%, failure to maintain appointments, etc.)
5. Physician Decision: If at any time the treating physician feels constraints of this protocol are detrimental to the patient's health remove the patient from protocol therapy.
6. Protocol Defined Delay:
  - Patients who experience a treatment-related toxicity causing a delay in treatment > 14 days
  - Delay in protocol > 28 days for major events or other non-treatment related delays
7. Death

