After recovery from surgical resection, patients will receive lapatinib post-operatively twice a day for two consecutive days every 7 days (2 days on/5 days off) in 28-day cycles.

Adequate recovery from surgical resection includes, but is not limited to, the following:

- No signs or symptoms of infections related to the surgical wound (*i.e.*, increasing erythema or cellulitis of the surrounding area, large amount of drainage, fever)
- Wound edges have healed

[figure not shown]
Post-operatively, patients must begin treatment within 30 days of surgical resection, and preferably within 3 weeks of the post-operative MRI; if more than 3 weeks elapse after the post-operative MRI, the patient will need a new MRI.

Patients will be followed by routine blood work, general and neurological examination, and MR imaging. See Section [9.1](#) for schedule.

Patients may continue to receive cycles of lapatinib until tumor progression, development of unacceptable toxicity, or meeting other criteria for going off treatment (Section [10.1](#)). Patients will be followed for adverse events for at least 30 days after the last dose of lapatinib. All patients will be followed for survival.

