- d) All measurable and non-measurable lesions must be assessed using the same techniques as baseline.
- e) The corticosteroid dose at the time of the scan evaluation should be no greater than the dose at time of baseline scan.
- f) Stable or improved non-enhancing (T2/FLAIR) lesions on same or lower dose of corticosteroids compared to baseline scan.
- g) Stable or improved clinically.

**Note:** Subjects with non-measurable disease cannot have a partial response. The best response possible is stable disease.

Stable Disease (requires all of the following):

- a) Does not qualify for CR, PR, or progression.
- b) The designation of stable disease requires a minimum of 4-week duration.
- c) All measurable and non-measurable sites must be assessed using the same techniques as baseline.
- d) Stable non-enhancing (T2/FLAIR) lesions on same or lower dose of corticosteroids compared to baseline scan. In the event that the corticosteroid dose was increased for new symptoms and signs without confirmation of disease progression on neuroimaging, and subsequent follow-up imaging shows that this increase in corticosteroids was required because of disease progression, the last scan considered to show stable disease will be the scan obtained when the corticosteroid dose was equivalent to the baseline dose.

e) Stable clinically.

Progressive Disease (defined by any of the following):

- a)  $\geq 25\%$  increase in sum of the products of perpendicular diameters of enhancing lesions compared to the smallest tumor measurement obtained either at baseline (if no decrease) or best response, on stable or increasing doses of corticosteroids.\*
- b) Significant increase in T2/FLAIR non-enhancing lesion on stable or increasing doses of corticosteroids compared to baseline scan or best response following initiation of therapy,\* not due to co-morbid events (radiation therapy, demyelination, ischemic injury, infection, seizures, postoperative changes, or other treatment effects).
- c) Any new lesion.
- d) Clear clinical deterioration not attributable to other causes apart from the tumor (e.g., seizures, medication adverse effects, complications of therapy, cerebrovascular events, infection, etc.) or changes in corticosteroid dose. The definition of clinical deterioration is left to the discretion of the treating physician, but it is recommended that a decrease in 20% of KPS or from any baseline to 50% or less be considered, unless attributable to comorbid events.

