- e) Failure to return for evaluation due to death or deteriorating condition.
- f) Clear progression of non-measurable disease.

\* Stable doses of corticosteroids include patients not on corticosteroids.

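### Section 10.1 item 1 defines progression for stopping lapatinib differently from Section 8.1: its growth limb has no steroid condition, and it has no T2/FLAIR or non-measurable limb

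*Combined protocol and SAP*

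**What the plan says.** Section 10.1 item 1 instructs sites: "Remove patient from protocol therapy at the time progressive disease is documented". It then defines progression as neurologic worsening that has no other explanation, or "a greater than 25% increase in the measurement of the tumor by MRI scan". A further sentence ends study treatment "If neurologic status deteriorates, on a stable or increasing dose of steroids, or if new lesions appear on serial MRI". Item 1 refers to neither Section 8.1 nor RANO. Death is listed separately, as item 7.

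Section 8.1 lets any one of six limbs define progressive disease. Limb (a) is growth of 25% or more in the summed products of diameters, "compared to the smallest tumor measurement obtained either at baseline (if no decrease) or best response, on stable or increasing doses of corticosteroids". A footnote adds: "Stable doses of corticosteroids include patients not on corticosteroids". Limb (b) is "Significant increase in T2/FLAIR non-enhancing lesion on stable or increasing doses of corticosteroids compared to baseline scan or best response". Limb (c) is a new lesion, (d) is clinical decline with no other cause, and (e) is not returning because of death or decline. Limb (f) is "Clear progression of non-measurable disease".

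Section 4.1 says, for both groups: "Patients may continue to receive cycles of lapatinib until tumor progression, development of unacceptable toxicity, or meeting other criteria for going off treatment". It cites Section 10.1 for those other criteria. Section 4.4 asks for a postoperative steroid taper to a stable dose, without a date for reaching it.

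**The concern.** Two definitions of progression bear on one decision, whether the patient stays on lapatinib, and they do not select the same patients. In a multicenter trial, two sites looking at the same scan could act differently while each follows the protocol. The mismatch runs both ways: item 1 is broader than 8.1 on enhancing growth, and narrower on non-enhancing and non-measurable disease.

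Limb (f) is relevant to this design. Every patient has a resection, and the response baseline in Section 8.1 is the MRI before the post-surgical cycles, not the pre-operative scan on which Section 3.2 requires measurable disease. Section 8.1 itself provides for patients whose disease is non-measurable. For them a percentage rule has no clear starting value, and residual disease that is already present is not a new lesion.

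**Working it through.** No formula applies, and the plan states no figure to reproduce. The check sets item 1 against each limb of Section 8.1.

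| 8.1 limb | Content | Section 10.1 item 1 | Differs? |
|---|---|---|---|
| (a) | Growth, steroid dose stable or rising | Growth, no steroid condition | Yes |
| (b) | T2/FLAIR increase | No counterpart | Yes |
| (c) | New lesion | Present | No |
| (d) | Clinical decline | Close counterpart | No |
| (e) | Failure to return | Not in item 1; item 7 covers death only | Yes |
| (f) | Non-measurable progression | No counterpart | Yes |

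Four of six limbs differ: (a), (b), (e) and (f). The measurement and the reference scan are not counted as differences, because Sections 8.1 and 8.2 supply them.

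**Case (a).** Because the footnote treats patients off corticosteroids as stable, the two growth rules separate only when the dose is still being reduced at the scan. Growth above 25% in such a patient does not satisfy 8.1(a), but item 1 requires removal. The discretion in Section 10.0 and in 10.1 item 5 is discretion to stop, so it cannot keep this patient on drug.

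**Case (b).** A patient whose only progression is under limb (b) or (f) has progressive disease by 8.1 and falls outside item 1's definition. A site working from item 1 is not obliged to stop. A site that reads tumor progression in Section 4.1 as 8.1 progression would stop, and any investigator may stop at discretion.

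**Timing.** MRI is scheduled before odd-numbered 28-day cycles (Section 9.1).

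- Scheduled gap between scans: 2 × 28 = 56 days, with a clinical examination before the even cycle at about 28 days.
- The pre-Cycle 3 scan may be up to 5 days early, so it falls 56 − 5 = 51 to 56 days after Cycle 1 starts.
- Cycle 1 must start within 30 days of surgery, so without delays that scan is at most 30 + 56 = 86 days after surgery.

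These are scheduled intervals and bound nothing. Section 4.4 recommends repeat imaging on suspected deterioration, and a steroid dose can also be reduced later in treatment.

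**Numbers affected.** The documents give no rate for either case, so no count can be estimated. The planned 18 + 15 = 33 patients is not a ceiling, because Sections 4.1 and 5.1 let replaced patients receive post-surgical lapatinib.

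**The case against.** The strongest defense is that item 1 is shorthand for 8.1. It opens with documented progressive disease, a term set out in full only in 8.1. A site that goes to 8.1(a) for the measurement and the reference scan finds the steroid condition in the same sentence. This does not hold for the steroid condition. Item 1 is silent on measurement and reference, so 8.1 can fill those gaps. It is not silent on steroids: it attaches a steroid condition to neurologic decline and leaves growth without one.

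A second defense is that item 1 speaks of the tumor, not of enhancing lesions, so a measured non-enhancing increase above 25% might fall within it. That is possible, but 8.1(b) asks for a significant increase with no percentage, and 8.1 confines measurable lesions to enhancing ones. The limb is not clearly there.

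A third is that a stopping rule need not equal a response rule, and that stopping on growth during a taper is cautious. That would be a fair choice if the plan stated it as one.

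The objection that Section 4.1 and discretion largely deal with case (b) does stand. A reader might infer that treatment has to continue after T2/FLAIR or non-measurable progression. The documents do not say so, and Section 4.1 offers a route to stopping. A reader might also infer that the steroid-taper case is common, or take 56 days as the extra exposure. The footnote narrows the first, no rate is given for it, and the second is only a scheduled interval.

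**Conclusion.** The inconsistency is real and minor. Item 1 as written requires removal of a patient who does not meet 8.1(a) when the steroid dose is falling. It also omits 8.1(b) and (f), and it leaves (e) partly to item 7.

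What it affects is time on treatment. Through that it also affects the period in which response is counted, because Section 11 counts responses occurring while the patient is on treatment. A reader might infer that the trial's main results or its PFS estimate are compromised. The documents do not support that: the primary PK and PD endpoints are measured in surgical tissue, and Section 11 gives PFS its own definition with a confirming scan.

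The conclusion on case (a) rests on reading item 1's explicit definition as operative. Case (b) further needs a site to apply that definition in preference to reading Section 4.1 through 8.1. How often either case would arise cannot be judged from the documents.

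**What to change.** Replace the definition in Section 10.1 item 1 with: progressive disease as defined in Section 8.1. If other clinical reasons for stopping are wanted, including growth seen while steroids are being reduced, list them as separate items so that they read as deliberate additions.

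The cost is one sentence of protocol wording, with no extra scans or patients. Optionally, add one case-report-form item at off-treatment recording which 8.1 limb was met; the schedule in Section 9.1 already collects the glucocorticoid dose with MRI.

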## 10.2 Off Study Criteria

Patients will only be off study at the time of death. All patients will be followed for survival every 2 months for the first two years from the off treatment date; after 2 years, patients will be followed every 6 months until death. Survival status may be obtained by phone call, clinic visit, or medical records (e.g. physician notes/laboratory results of clinic or hospital visit).

## 11.0 STATISTICAL CONSIDERATIONS

This is an open-label, multicenter, early phase clinical trial to evaluate whether lapatinib, when given on a pulsatile dosing schedule, will reach an intratumoral concentration of 1.5  $\mu\text{M}$  or higher in 70% of patients with recurrent and surgically accessible EGFR-amplified high-grade glioma. It will also determine whether this lapatinib dosing regimen will achieve 80% reduction in ratio of phosphorylated to total EGFR in tumor tissue in 70% of patients with recurrent and surgically accessible EGFR-amplified high-grade glioma.

### Primary Endpoints:

- Lapatinib intratumoral concentration (PK)
- Ratio of pEGFR/total EGFR (PD) in tumor tissue

